Measure	Variable	Population	Analysis Timepoint	Treatment Comparisons	Analysis Method	Analysis Type
Disease flare	Proportion of patients with disease flare	DBW	Week 16 to Week 44	Baricitinib versus placebo	Logistic regression	Secondary analysis
PedACR response	PedACR30/50/70/90/100 response rates (compare to patient's condition prior to first dose of investigational product)	Safety/PK, OLLI, OLLI2	Week 2 to Week 12	No comparison	Summary statistics	Secondary analysis
		DBW	Week 16 to Week 44	Baricitinib versus placebo	Logistic regression	Secondary analysis
Active joint count	Change from baseline of active joint count	OLLI2	Week 2 to Week 12	No comparison	Summary statistics	Secondary analysis
		DBW	Week 16 to Week 44	Baricitinib versus placebo	ANCOVA MMRM	Secondary analysis Supplementary analysis
Limited of range motion joint count	Change from baseline of limited range of motion joint count	OLLI2	Week 2 to Week 12	No comparison	Summary statistics	Secondary analysis
		DBW	Week 16 to Week 44	Baricitinib versus placebo	ANCOVA MMRM	Secondary analysis Supplementary analysis
Physician's global assessment of disease activity	Change from baseline of physician's global assessment of disease activity	OLLI2	Week 2 to Week 12	No comparison	Summary statistics	Secondary analysis
		DBW	Week 16 to Week 44	Baricitinib versus placebo	ANCOVA MMRM	Secondary analysis Supplementary analysis
Physical function as measured by CHAQ	Change from baseline of physical function	OLLI2	Week 2 to Week 12	No comparison	Summary statistics	Secondary analysis
		DBW	Week 16 to Week 44	Baricitinib versus placebo	ANCOVA MMRM	Secondary analysis Supplementary analysis

Description of Analysis Period and Analysis Method of Secondary Endpoint and Health Outcome

Measure	Variable	Population	Analysis Timepoint	Treatment Comparisons	Analysis Method	Analysis Type
Parent's global assessment of overall well-being as measured by CHAQ	Change from baseline of parent's global assessment of overall well-being	OLLI2	Week 2 to Week 12	No comparison	Summary statistics	Secondary analysis
		DBW	Week 16 to Week 44	Baricitinib versus placebo	ANCOVA	Secondary analysis
					MMRM	Supplementary analysis

Description of Analysis Period and Analysis Method of Secondary Endpoint and Health Outcome

Measure	Variable	Population	Analysis Timepoint	Treatment Comparisons	Analysis Method	Analysis Type
hsCRP (mg/L)	Change from baseline of hsCRP	OLLI2	Week 2 to Week 12	No comparison	Summary statistics	Secondary analysis

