6.1. Inclusion Criteria

Patients are eligible to enroll in the study only if they meet all of the following criteria at screening and at baseline:

Patient and Disease Characteristics

- [1] Are at least 2 years and less than 18 years of age; full date of birth will be collected except in countries in which it is not allowed.
- [2] Have a diagnosis with onset before the age of 16 years of any of the following forms of JIA as defined by ILAR criteria:
 - Polyarticular JIA (positive or negative for RF)
 - Extended oligoarticular JIA
 - ERA
 - JPsA
- [3] Have had an inadequate response or intolerance to treatment with ≥ 1 conventional or bDMARD. Patients must have been treated for at least 12 weeks before inadequate response may be determined.
- [4] Patients with polyarticular JIA or extended oligoarticular JIA must have at least 5 active joints at screening and baseline. Those with JPsA must have at least 3 active joints at screening and baseline. Those with ERA must have (a) at least 3 active joints at screening and baseline or (b) involvement of at least 1 sacroiliac joint AND a physician global assessment of at least 3 (on the 21-circle numeric rating scale [NRS]). Active joint is defined as the presence of joint swelling or, in the absence of swelling, joints with limitation of motion plus pain on motion and/or tenderness on palpation.

Informed Consent

- [5] Both the child or adolescent and a parent or legal guardian are able to understand and fully participate in the activities of the clinical study and sign their assent and consent, respectively, accordance to local guidelines.

Contraception

- [6] Male or nonpregnant, nonbreastfeeding female patients

Patients of child-bearing potential who are abstinent (if this is complete abstinence, as their preferred and usual lifestyle).

Total abstinence is defined as refraining from intercourse during the entirety of the study and for at least 1 week following the last dose of investigational product. Periodic abstinence such as calendar, ovulation, symptothermal, post-ovulation methods and withdrawal are not acceptable methods of contraception.

Otherwise, patients and their partners of childbearing potential must agree to use 2 effective methods of contraception, where at least 1 form is highly effective for the entirety of the study and for at least 1 week following the last dose of investigational product.

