10.3.3. Efficacy Analyses

10.3.3.1. Primary Analyses

The primary efficacy endpoint is time to disease flare (flare defined as worsening of $\geq 30\%$ in at least 3 of the 6 PedACR core criteria for JIA and an improvement of $\geq 30\%$ in no more than 1 of the criteria) during the DBW period for the DBW population. If either the number of joints with active arthritis or the number of joints with limitation of motion are used in the calculation of flare for a study visit, then a minimum worsening of at least 2 active joints or 2 joints with limitation of motion must be present. An active joint is defined as a joint with swelling or, in the absence of swelling, limitation of motion accompanied by pain on motion and/or tenderness. If either the Physician's Global Assessment of Disease Activity or the Parent's Global Assessment of Well-Being are used in the calculation of flare for a study visit, then a minimum worsening (as defined in the SAP) on the visual analogue scale (VAS) must be present. If ESR or CRP is used in the definition of "flare" and counts towards worsening, then the second value for ESR or CRP used in the calculation must be above the upper limit of normal for ESR (>20 mm/hour) or CRP. In JAHV, for primary analysis, disease flare definition will only use ESR.

The 6 PedACR core criteria (Gianni et al. 1997) includes:

- Number of active joints (defined as a joint that is swollen or in the absence of swelling has loss of passive motion accompanied by either pain on motion or joint tenderness) in 73 joints
- Number of joints with limited range of motion in 69 joints
- Physician's Global Assessment of Disease Activity
- Parent's Global Assessment of Well-Being
- Physical function as assessed by the CHAQ
- Acute-phase reactant (hsCRP and ESR)

Patients who discontinue the DBW period without experiencing a flare will have their data censored. A stratified logrank test across all JIA subtypes will be used as the primary analysis method. Survival curves will be estimated using the Kaplan–Meier method for all "time-to" variables in the DBW period.

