Physical function as measured by CHAQ (0-3)	
The Childhood Health Assessment Questionnaire (CHAQ) assesses health status and physical function over the past week in children with juvenile arthritis over the past week, which the parent or legal guardian completes, regardless of the age of the patient.
 
Physical function is measured by CHAQ from disability index. The Disability Index contains 30 items grouped into the following 8 domains (not including assistive devices/aids questions): physical function, dressing, and grooming (4 items), arising (2 items), eating (3 items), walking (2 items), hygiene (5 items), reach (4 items), grip (5 items), and activities (5 items). Each item is scored from 0 to 3 (0 = no difficulty; 1 = some difficulty; 2 = much difficulty; 3 = unable to do or not applicable) (Singh et al. 1994). The total score is the average of domain score, which is range from 0 to 3.
 
At least 6 domains are required in calculation.
	Change from baseline of physical function	
The details of physical function calculations are documented in separate CHAQ instruction document.
 
Calculation: Change from baseline: observed score at visit minus baseline score
	Missing if baseline or postbaseline value is missing. LOCF will be applied for post baseline missing values.
hsCRP (mg/L)	The hsCRP test is a highly sensitive quantification of C-Reactive protein (CRP), an acute-phase protein that increases during inflammation.	Change from baseline of hsCRP	Calculation: Change from baseline: observed lab value at visit minus baseline lab value	Missing if baseline or postbaseline value is missing. LOCF will be applied for post baseline missing values.

Secondary Efficacy Endpoint Analyses

Measure	Description	Variable	Derivation/Comment	Imputation Approach if with Missing Components
ESR (mm/hr)	An erythrocyte sedimentation rate (ESR) is a type of blood test that measures how quickly erythrocytes (red blood cells) settle at the bottom of a test tube that contains a blood sample. Normally, red blood cells settle relatively slowly. A faster-than-normal rate may indicate inflammation in the body.	Change from baseline of ESR	Calculation: Change from baseline: observed lab value at visit minus baseline lab value	Missing if baseline or postbaseline value is missing. LOCF will be applied for post baseline missing values.

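### Scoring a CHAQ item 3 when it is 'not applicable' understates percentage change in the CHAQ component of PedACR response and flare for any child to whom an item does not apply; the size cannot be fixed from the documents.

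*SAP*

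**What the plan says.** The CHAQ scoring is described in Protocol 9.1.5 and again in SAP 6.10.2, Table JAHV.6.4. Both run the item scale from 0 to 3 and define the top score in identical words: "3 = unable to do or not applicable". The SAP adds the structure: "The Disability Index contains 30 items grouped into the following 8 domains", and "The total score is the average of domain score, which is range from 0 to 3". It sets a minimum, "At least 6 domains are required in calculation", and sends the rest elsewhere: "The details of physical function calculations are documented in separate CHAQ instruction document". Neither document says how items combine into a domain score, or how a not-applicable answer relates to the six-domain minimum.

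On age, Protocol 6.1 admits patients who "Are at least 2 years and less than 18 years of age". The CHAQ is a form "which the parent or legal guardian completes, regardless of the age of the patient", and no age adaptation is described.

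On use, Protocol 10.3.3.1 lists "Physical function as assessed by the CHAQ" among the six core criteria. Flare requires worsening of at least 30% in three of the six from the value at randomization. PedACR30 requires improvement of at least 30% in three of the six from the pre-dose baseline. CHAQ change from baseline is also a secondary endpoint.

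**The concern.** An activity that a child does not perform for reasons other than arthritis carries no information about arthritis. Scoring it 3 adds a block of disability that stays put while the true disease moves. A constant does no harm to a simple difference, but both composite endpoints are built on percentage change, and there it inflates the denominator.

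The issue is most plausible in the youngest age groups. The protocol recognises age limits for its other questionnaires: section 9.1.5 describes CHQ-PF50 as covering ages 5 to 18 and exempts children under 4 from EQ-5D-Y. For CHAQ, an item outside a child's range is turned into the worst score.

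At stake is the sensitivity of one of the six components that decide entry to randomization and the primary flare endpoint. CHAQ has no absolute floor in the flare rule, unlike the joint counts, the two global assessments and ESR, so it can supply the third criterion in a child with low residual activity. The age-group analyses of the primary endpoint listed as possible in SAP 6.16 would also carry any scoring artefact that varies with age.

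**Working it through.** **Inputs from the documents.** Not-applicable items score 3 (Protocol 9.1.5; SAP Table JAHV.6.4). There are 8 domains, and the total is their mean, 0 to 3. The SAP's item counts agree with its total: 4 + 2 + 3 + 2 + 5 + 4 + 5 + 5 = 30. The threshold is 30% relative change. The plan gives no other CHAQ figure to reproduce.

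**Assumed inputs.** The number of not-applicable items, the mean score m of the applicable content, and the item-to-domain rule. Two domain rules are tried because the documents give none.

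**Formula.** Let f be the share of the total score's weight held by not-applicable items. The recorded score is

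S = (1 − f)m + 3f.

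If the applicable content changes by a proportion t, the recorded proportional change is

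t × (1 − f)m / [(1 − f)m + 3f].

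The multiplier is below 1 whenever f > 0. The true change needed to record 30% is 0.30 divided by the multiplier.

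**Rule A: the worst item sets the domain.** One not-applicable item fixes its domain at 3. With k fixed domains, f = k/8 and the multiplier is (8 − k)m / [(8 − k)m + 3k].

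| k | m | Multiplier | True change needed to record 30% |
|---|---|---|---|
| 1 | 0.5 | 3.5/6.5 = 0.538 | 56% |
| 1 | 1.0 | 7/10 = 0.70 | 43% |
| 2 | 0.5 | 3/9 = 0.333 | 90% |
| 2 | 1.0 | 6/12 = 0.50 | 60% |

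- Worsening, k = 2: applicable content rises from 0.50 to 0.75 (+50%). The score moves from (6 × 0.50 + 6)/8 = 1.125 to (6 × 0.75 + 6)/8 = 1.3125, or +16.7%, and does not count.
- Improvement, k = 2: applicable content falls from 1.0 to 0.5 (−50%). The score moves from 1.50 to 1.125, or −25%, and misses 30%.
- Ceiling, k = 2, m = 1.5: full recovery records 9/15 = 60%, so CHAQ cannot count towards PedACR70 or higher.

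**Rule B: the domain is the mean of its items.** Take one not-applicable item of four in each of two domains: f = 2 × 0.25/8 = 0.0625.

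- m = 0.5: 0.46875/0.65625 = 0.714. A 67% worsening records 48%, which still counts.
- m = 1.0: 0.9375/1.125 = 0.833. A 50% improvement records 42%, which still counts.
- A single item in one five-item domain (f = 1/40, m = 1.0): 0.975/1.05 = 0.929. A true 30% records 27.9%; 32% is needed.

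**Absolute change.** S₁ − S₀ = (1 − f)(m₁ − m₀). The offset 3f cancels in the ANCOVA of change from baseline. What remains is a scaling by (1 − f), and change inside a domain fixed at 3 is lost.

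**With not-applicable items left out.** f = 0, the multiplier is 1, and a true 30% records 30%. The six-domain minimum allows up to 8 − 6 = 2 domains to be unscored.

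**The case against.** The strongest reply is that the operative algorithm is not in these documents. The SAP defers to a separate CHAQ instruction document, and the six-domain minimum shows that domains can go unscored, so not-applicable items may already be excluded in practice. This limits what can be claimed about the scores actually produced, but it does not remove the point. If the instruction document follows the printed rule, the score is biased; if it contradicts the rule, Protocol 9.1.5 and the SAP table are wrong and need correcting.

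It can also be said that no item wording is given, so nobody can tell from the documents which items fail to apply at which age, or how often a parent would answer that way. That stands. The 2 to <6 Safety/PK cohort was still to be initiated in Protocol Appendix 7, and no randomized count by age is given.

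A reader might infer that young children in general carry a large fixed block of false disability, that their CHAQ component becomes insensitive, and that the treatment difference is measurably diluted. The documents do not support this. The large figures need an unstated worst-item rule and assumed counts. Under item averaging, the 67% and 50% examples still cross 30%. Flare needs three of six criteria, so five others remain. The damping also blunts the disqualifying limbs (30% improvement for flare, more than 30% worsening for PedACR). The block is fixed only while the item stays not applicable: a child who grows into the activity would show an apparent improvement.

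**Conclusion.** The point holds as a stated scoring rule that gives the wrong score for a child with at least one not-applicable item. The recorded percentage change in CHAQ is then too small under either domain rule. The direction of that damping follows from the arithmetic; its size does not follow from the documents. It ranges from slight (30% recorded as 27.9%) to severe (90% needed to record 30%), depending on the domain rule, the number of such items and the level of true disability, all of which are assumptions here.

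The consequence for the primary endpoint is indirect and probably modest. The same rule applies in both arms, so the risk is lost sensitivity, mainly in the youngest children, and not a false-positive result. No loss of power can be calculated, because the share of flares that would be missed is unknown. The secondary analysis of absolute CHAQ change is less affected, since the offset itself cancels.

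**What to change.** In Protocol 9.1.5 and SAP Table JAHV.6.4, reserve the score of 3 for inability and state that not-applicable items are not scored. State the item-to-domain rule, score each domain from its applicable items, treat a domain with none as missing, and apply the existing six-domain minimum. Bring the CHAQ instruction document and the flare and PedACR algorithm document into line.

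On-site PedACR30 and flare results have already governed randomization and discontinuation, so keep those decisions as made. Where not-applicable answers were captured separately from inability, report PedACR30, flare and CHAQ change under both scorings, by age group, as a sensitivity analysis. If they were not captured separately, say so as a limitation.

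The cost is a short text change plus programming. There are two downsides: a few very young children may have fewer than six scorable domains and so a missing CHAQ component, and the set of scored items may differ between visits as a child grows.

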9.1.2.1. PedACR30/50/70/90/100 Assessments

The PedACR30 consists of the 6 core criteria listed below. The definition of improvement is at least 30% improvement from baseline in 3 of any 6 variables in the core set, with no more than 1 of the remaining variables worsening by >30%. Pediatric ACR50 and ACR70 improvement criteria are defined as above with improvements of 50% and 70%, respectively.

- Number of active joints (defined as a joint that is swollen or in the absence of swelling has loss of passive motion accompanied by either pain on motion or joint tenderness) in 73 joints
- Number of joints with limited range of motion in 69 joints
- Physician's Global Assessment of Disease Activity (21-circle visual analogue scale [VAS]) (Section 9.1.2.7)
- Parent's Global Assessment of Well-Being (Section 9.1.5)
- Physical function as assessed by the Childhood Health Assessment Questionnaire (CHAQ) (Section 9.1.5)
- Acute-phase reactant (hsCRP and ESR)

ACR50, ACR70, ACR90, and ACR100 responses are efficacy measures that are calculated as improvements of at least 50%, 70%, 90% and 100%, respectively, in the PedACR Core Set values listed above.

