9.1.2.3. Disease Activity

Minimal Disease Activity

Minimal disease activity is calculated based on the scores from the Physician's Global Assessment of Disease Activity (Section 9.1.2.7), Parent's Global Assessment of Well-Being (Section 9.1.5), and the number of swollen joints as described in the SAP and Consolaro et al. 2012.

Inactive Disease

Inactive disease is indicated by the presence of all of the following (Wallace et al. 2011):

- No joints with active arthritis based on JADAS-27 (Section 9.1.2.1)
- No fever, rash, serositis, splenomegaly, hepatomegaly, or generalized lymphadenopathy attributable to JIA as assessed by the investigator
- No active uveitis as assessed by the investigator
- Normal erythrocyte (ESR) or hsCRP (i.e., within normal limits in the local laboratory or, if elevated, not attributable to JIA)
- Physician's Global Assessment of Disease Activity indicating no active disease (best possible score on scale [0]) (Section 9.1.5)
- Duration of morning stiffness ≤ 15 minutes

Remission

Remission is defined as inactive disease for at least 24 consecutive weeks (Wallace et al. 2012).

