
Inactive disease
	
Inactive disease is indicated by the presence of all of the following (Wallace et al. 2011):
 
 No joints with active arthritis based on JADAS-27 No fever, rash, serositis, splenomegaly, hepatomegaly, or generalized lymphadenopathy attributable to JIA as assessed by the investigator No active uveitis as assessed by the investigator Normal erythrocyte (ESR) or hsCRP (ie, within normal limits in the local laboratory or, if elevated, not attributable to JIA) Physician's Global Assessment of Disease Activity indicating no active disease (best possible score on scale [0]) Duration of morning stiffness less than 15 minutes In inactive disease analysis as secondary endpoint, ESR measure is used as acute-phase reactant measure. 	
Proportion of patients who achieved inactive disease
	
 Step 1: If joint with active arthritis isn't 0, stop; else Step 2: If there is fever, rash, serositis, splenomegaly, hepatomegaly, or generalized lymphadenopathy attributable, stop; else Step 3: If uveitis, stop; else Step 4: If ESR>20, stop; else Step 5: If physician's global assessment of disease activity isn't 0, stop; else Step 6: If stiffness >15min, stop; else Step 7: Conclude the patient achieved inactive disease status. 	
Missing if any component is missing. NRI will be applied to missing data.

Secondary Efficacy Endpoint Analyses

Measure	Description	Variable	Derivation/Comment	Imputation Approach if with Missing Components
Minimal disease activity	Minimal disease activity is calculated based on the scores from the Physician's Global Assessment of Disease Activity, Parent's Global Assessment of Patient's overall Well-Being, and the number of swollen joints as described in Consolaro et al. 2012.	Proportion of patients who achieved minimal disease activity	
 • if physician's global assessment of disease activity ≤ 3.5, and • if parent's global rating of patient's overall well-being ≤ 2.5, and • if swollen joint count ≤ 1, then conclude the patient reaches minimal disease activity; all else conclude the minimal disease activity is not reached. 	
Component is missing if baseline or postbaseline value is missing. LOCF will be applied for post baseline missing values.
 
If all components are missing after LOCF, NRI will be applied to missing data.

Secondary Efficacy Endpoint Analyses

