JADAS-27	
The JADAS-27 score is a validated composite disease activity measure for JIA (Consolaro et al. 2012). Recently, the scoring system was adapted to use the 27-joint count (Bazso et al. 2009) and hsCRP or ESR for the inflammatory marker component (Nordal et al. 2012). The JADAS 27 includes the following joints: cervical spine, elbows, wrists, metacarpophalangeal joints (from first to third), proximal interphalangeal joints, hips, knees, and ankles. In JADAS-27 analysis as secondary endpoint, ESR measure is used as acute-phase reactant measure,
	
Change from baseline of JADAS-27 score
	
JADAS-27 score (0-57) will be determined based on 4 components:
 
 • PHY: Physician’s Global Assessment of Disease Activity (0-10 VAS) • PGA: Parent’s Global Assessment of Patient’s overall Well-Being (0-100 mm VAS) • Joint27: Number of joints with active disease (27-joint assessment) • ESR (mm/hr) 
Calculation:
 
NormESR: Normalized ESR (0-10) NormESR=(ESR-20)/10
 
Scaled PGA= scaled Parent’s Global Assessment of Patient’s overall Well-Being (0-10) Scaled PGA=PGA/10
 
JADAS(ESR)27=PHY+ScaledPGA+Joint27+NormESR
 
Change from baseline: observed JADAS(ESR)-27 at visit minus baseline JADAS-27
	
Missing if baseline is missing: For observed value, missing if all the components are missing. LOCF will be applied for post baseline missing value. If at least one component is non-missing, LOCF will be applied on the missing components prior to LOCF being applied to the composite score

Secondary Efficacy Endpoint Analyses

Measure	Description	Variable	Derivation/Comment	Imputation Approach if with Missing Components
Pain (VAS)	The pain assessment item will be collected from the CHAQ.	Change from baseline of pain vas score	Calculation: Change from baseline: observed score at visit– baseline score	Missing if baseline or postbaseline value is missing. LOCF will be applied for post baseline missing value.

Abbreviations: CHQ-PF50 = Child Health Questionnaire-Parent Form 50; ESR = erythrocyte sedimentation rate; hsCRP = high-sensitivity C-reactive protein; JADAS = Juvenile Arthritis Disease Activity Score; JIA = juvenile idiopathic arthritis; LOCF = last observation carried forward; NRI = nonresponder imputation; PedACR = Pediatric American College of Rheumatology; VAS = Visual Analog Scale.

Table JAHV.6.5. Description of Analysis Period and Analysis Method of Secondary Endpoint and Health Outcome

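### Inactive disease is defined on 27 joints although 73 are counted at each visit, and the derivation step names neither set; inactive-disease and remission rates can be overstated, probably slightly.

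*SAP*

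**What the plan says.** Two joint counts are in use.

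- **The 73-joint count.** The active-joint component of the PedACR core set is counted over 73 joints: "either pain on motion or joint tenderness) in 73 joints" (protocol 9.1.2.1, repeated in protocol 10.3.3.1 and in the active-joint row of SAP Table JAHV.6.4). Table JAHV.2 of the protocol marks joint assessment at screening, at every OLLI and DBW visit, at early termination and at follow-up.
- **The 27-joint count.** JADAS-27 uses "Number of joints with active disease (27-joint assessment"), and the joints are listed as "cervical spine, elbows, wrists, metacarpophalangeal joints (from first to third), proximal interphalangeal joints, hips, knees, and ankles".

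The joint item of inactive disease is tied in words to the second count. The SAP description column (Table JAHV.6.4) has "No joints with active arthritis based on JADAS-27". The protocol has "No joints with active arthritis based on JADAS-27 (Section 9.1.2.1"), but JADAS-27 is described in 9.1.2.2; Section 9.1.2.1 holds the 73-joint PedACR count. The SAP derivation column opens Step 1 with "If joint with active arthritis" and requires the number to be 0, without naming a joint set.

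Remission is built on inactive disease held for 24 consecutive weeks (protocol 9.1.2.3). Table JAHV.6.4 checks it over six preceding visits. The hsCRP versions of both endpoints (SAP Tables JAHV.6.6 and JAHV.6.7) keep the same logic and change only the laboratory item.

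**The concern.** The endpoint's label promises that no joint is active, but the written rule examines only part of the joints that the trial counts. One child at one visit can have an active-joint count of 1 or more in the PedACR data and still pass the joint item of inactive disease. Remission inherits the gap.

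The text also leaves the programmer a choice. The description column points to 27 joints, the protocol's section number points to 73, and Step 1 is silent. Two programmers could derive different endpoints from the same plan.

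What is at stake is mainly the absolute rate and its meaning. In the OLLI period, inactive disease is summarised without a comparator (protocol Table JAHV.8, SAP Table JAHV.6.5), so the rate is the result and any misclassification goes straight into it.

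**Working it through.** **1. Reproduce the plan's own figures.** Count the joints listed for JADAS-27, taking both sides and five proximal interphalangeal joints per hand:

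cervical spine 1 + elbows 2 + wrists 2 + first to third metacarpophalangeal 6 + proximal interphalangeal 10 + hips 2 + knees 2 + ankles 2 = 27.

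The SAP gives the score range in "JADAS-27 score (0-57) will be determined based on 4 components". Physician global 10 + parent global 10 + joints 27 + normalised ESR 10 = 57. Both figures reproduce, so the 27-joint set is what the text says it is.

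**2. Joints counted but not checked.** 73 − 27 = 46, and 46/73 = 63%. The documents do not itemise the 73. If any of the 27 were not among them, more than 46 would be left out, so 46 is a minimum. The fourth and fifth metacarpophalangeal joints and the shoulders, for example, are not on the 27-joint list. Nor are the sacroiliac joints, through which some children with enthesitis-related disease can enter; whether these are among the 73 is not stated.

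**3. What else must hold.** SAP Table JAHV.6.4 requires all of the following as well: no systemic features attributable to JIA, no active uveitis, ESR not above 20, physician global of 0, and morning stiffness not above 15 minutes. None of these examines the other joints directly. The physician global comes closest. It is scored by the Physician Assessor, while joints are counted by a separate Joint Assessor who is asked not to discuss disease activity with other site staff (protocol Section 9). The Physician Assessor does have access to efficacy data and source documents. A global of 0 alongside a recorded active joint is therefore possible, but should be uncommon.

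**4. Size.** The documents give no inactive-disease rate and no frequency of arthritis confined to joints outside the 27, so the effect cannot be computed. The following is an illustration on assumed values only: 64 per arm, 27-joint rates of 40% and 25%, and a share q of those children, equal in both arms, with an active joint only outside the 27. The 73-joint rate is the 27-joint rate × (1 − q), and the number misclassified is 64 × rate × q.

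| q (assumed) | 73-joint rates | Children misclassified per arm |
|---|---|---|
| 5% | 38.0% vs 23.8% | 1.3 vs 0.8 |
| 10% | 36.0% vs 22.5% | 2.6 vs 1.6 |
| 20% | 32.0% vs 20.0% | 5.1 vs 3.2 |

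With assumed rates of 30% and 20%, the numbers misclassified are 1.0 vs 0.6, 1.9 vs 1.3 and 3.8 vs 2.6. Given step 3, low values of q are the more plausible.

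**5. With the 73-joint count in Step 1**, the number of assessed joints left unchecked falls from at least 46 to 0.

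**The case against.** The best defence has four parts.

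- **The other items do most of the work.** A child with an active joint must also be given the best possible physician global and meet the ESR, stiffness, uveitis and systemic items. For remission this must recur at each of the six visits checked. This stands, and it is why the effect is probably small. It does not remove the gap: the joint item is listed as a separate requirement and should not depend on the global to catch the joints it leaves out.
- **The reduced count is a prespecified choice of a measure described as validated.** This stands in part. The documents call JADAS-27 validated as a disease activity score, but they give no reason for using its joint set to establish that no joint is active. Whether the cited criteria allow a reduced count cannot be checked from the documents, and nothing here relies on it.
- **The conflict may be only a slip.** The same protocol list sends the physician global to 9.1.5, although it is defined in 9.1.2.7, so the wrong section number may mean nothing. That is fair. It is also possible that Step 1 would be programmed on the full count: it does not use the SAP's named 27-joint variable, and its wording resembles the flare rule, which rests on 73 joints. In that case no misclassification arises, but the description would then be wrong. Either way the text needs settling.
- **The consequences are limited.** Change in the 73-joint active count is analysed separately, so residual arthritis stays visible, and these are secondary endpoints without multiplicity control. This stands.

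A reader might go further and infer that 63% of children with a residual active joint would be reported as inactive. The documents do not support that. The 63% is a share of joints; using it as a probability would assume that arthritis is equally likely in every joint, and it ignores every other item in the definition.

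**Conclusion.** The point holds as a definition problem in two secondary endpoints and their hsCRP versions. The written rule leaves at least 46 of 73 counted joints unchecked, the derivation step does not say which count applies, and a child with a recorded active joint can be classed as having inactive disease or, if it persists, as in remission. Absolute rates can therefore be overstated. The amount is unknown and probably small; the figures in the illustration rest on assumed rates and assumed shares.

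Two stronger conclusions are not supported. The documents do not show that the rates are in fact overstated, since they contain no data on arthritis confined to the other joints. Nor do they show bias in favour of baricitinib: the same rule applies in both arms. The primary endpoint, time to flare, and the PedACR responses use the 73-joint count and are unaffected.

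**What to change.** 1. In SAP Table JAHV.6.4, Step 1, and in protocol 9.1.2.3, state that the active-joint count over all 73 assessed joints must be 0 for inactive disease, and hence for remission. Apply the same rule to the hsCRP versions.
2. Correct the protocol cross-reference, and align the SAP description column with Step 1.
3. Keep the 27-joint count for the JADAS-27 score, and report inactive disease and remission on 27 joints as a sensitivity analysis.

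If the sponsor prefers to keep 27 joints as the main version, Step 1 should say so with a reason, and the 73-joint version should be reported beside it. The choice should be fixed before database lock.

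The cost is one derivation line on data already collected, plus one extra display. The only downside is slightly lower inactive-disease and remission rates. If the sponsor judges that no principal feature of the protocol changes, protocol 10.3.1 allows the change and its justification to be recorded in the clinical study report without an amendment.
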